8.2.4. Adverse Events

The investigator or site staff will be responsible for detecting, documenting and reporting events that meet the definition of an AE or SAE.

8.2.4.1. Definition of an AE

An AE is any untoward medical occurrence in a subject administered a pharmaceutical product, biologic (at any dose), or medical device, which does not necessarily have a causal relationship with the treatment. Therefore, an AE can be any unfavorable and unintended sign (including an abnormal laboratory finding), symptom, or disease temporally associated with the use of a medical product, whether or not considered related to the medical product. AEs may include the onset of new illness and the exacerbation of pre-existing conditions.

The routine evolution of the disease condition under treatment according to the protocol will be evaluated as part of the disease symptoms assessments. Changes in the disease condition may not qualify as AEs. However, if there is a clinically relevant worsening of a sign or symptom of the condition under treatment and the outcome fulfills the definition of an AE, it must be reported as directed in the protocol.

8.2.4.2. Definition of a SAE

A serious adverse event is any untoward medical occurrence that, at any dose:

- a. Results in death
- b. Is life-threatening

NOTE: The term 'life-threatening' in the definition of 'serious' refers to an event in which the subject was at risk of death at the time of the event. It does not refer to an event, which hypothetically might have caused death, if it were more severe.

- c. Requires hospitalization or prolongation of existing hospitalization

NOTE: In general, hospitalization signifies that the subject has been detained (usually involving at least an overnight stay) at the hospital or emergency ward for observation and/or treatment that would not have been appropriate in the physician's office or out-patient setting. Complications that occur during hospitalization are AEs. If a complication prolongs hospitalization or fulfills any other serious criteria, the event is serious. When in doubt as to whether "hospitalization" occurred or was necessary, the AE should be considered serious.

Hospitalization for elective treatment of a pre-existing condition that did not worsen from baseline is not considered an AE.

- d. Results in disability/incapacity, or

NOTE: The term disability means a substantial disruption of a person's ability to conduct normal life functions. This definition is not intended to include experiences of relatively minor medical significance such as uncomplicated headache, nausea, vomiting, diarrhea, influenza, and accidental trauma (e.g., sprained ankle) which may interfere or prevent everyday life functions but do not constitute a substantial disruption.

- e. Is a congenital anomaly/birth defect.
- f. Medical or scientific judgment should be exercised in deciding whether reporting is appropriate in other situations, such as important medical events that may not be immediately life-threatening or result in death or hospitalization but may jeopardize the subject or may require medical or surgical intervention to prevent one of the other outcomes listed in the above definition. These should also be considered serious. Examples of such events are invasive or malignant cancers, intensive treatment in an emergency room or at home for allergic bronchospasm, blood dyscrasias or convulsions that do not result in hospitalization, or development of drug dependency or drug abuse.

8.2.5. Laboratory and Other Safety Assessment Abnormalities Reported as AEs and SAEs

Any abnormal laboratory test results (hematology, clinical chemistry, or urinalysis) or other safety assessments (e.g., ECGs, vital signs measurements), including those that worsen from baseline, and felt to be clinically significant in the medical and scientific judgment of the investigator are to be recorded as AEs or SAEs.

However, any clinically significant safety assessments that are associated with the underlying disease, unless judged by the investigator to be more severe than expected for the subject's condition, are **not** to be reported as AEs or SAEs.

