7.6. Treatment Compliance

Dosing compliance will be assessed at each clinic visit through subject interview and comparison of the amount of study medication the subject was scheduled to take over the number of days during the study with the amount returned.

The investigator may choose to interrupt or discontinue the study medication in case of an AE. Any interruption in dosing for this, or other reasons, must be documented.

The investigator should discontinue the study medication if continued administration of the study medication is believed to be contrary to the best interest of the subject. The reasons for discontinuation must be documented.

If the reason for the interruption or discontinuation of the study medication is an AE, an abnormal assessment (e.g., ECG finding), or a laboratory test abnormality, this information will be recorded as an AE.

If the subject is not compliant with the study medication administration, the investigator may need to evaluate whether the noncompliance should warrant subject withdrawal from the study.

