8.2.12.1. Physical Examination

All subjects will undergo a complete physical examination at Baseline (Visit 1) and each subsequent scheduled visit. Any clinically significant abnormal observation, newly emerged or worsened after the start of the subject's first dose of study medication in the current study, should be reported as an AE.

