8.2.12.3. ECG

A standard 12-lead ECG will be performed at every scheduled visit. Subjects will rest for approximately 5 minutes before the ECG recording begins and will be supine throughout the ECG evaluation. Significant findings not present prior to start of treatment, which meet the definition of an AE, must be recorded in the CRF.

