8.2.12.4. Clinical Laboratory Tests

If any results from the Baseline Visit (Visit 1) demonstrate, in the investigator's opinion, a clinically significant abnormality that the subject has not previously experienced, then the subject should be asked to return as soon as possible but no later than 3 months of the Baseline Visit for an unscheduled visit so that repeat specimens can be obtained.

The collection, processing and shipment of clinical laboratory samples will be fully described in the study laboratory manual. The parameters measured in these samples are described below.

The investigator (or his/her designee) will review each laboratory report from the central laboratory and assess any out of range lab results as "not clinically significant" (NCS) or "clinically significant" (CS). Any results which are considered clinically significant should be confirmed in a repeat test at the investigator's discretion. The investigator should consider repeat testing of persistent clinically significant results until the analyte returns to normal, or until an etiology is determined. The investigator (or his/her designee) will sign and date all laboratory reports.

Clinically significant laboratory abnormalities must be reported as an AE or SAE as appropriate.

Serum Chemistry

The serum chemistry parameters in [Table 3](#) will be assessed at every visit. Subjects are required to fast for approximately 8 or more hours prior to the serum chemistry being performed.

Table 3: Serum Chemistry Parameters

Alanine aminotransferase (ALT)	Creatinine, serum
Alkaline phosphatase	Gamma –glutamyltransferase (GGT)
Aspartate aminotransferase (AST)	Glucose
Albumin	Lactate dehydrogenase (LDH)
Bilirubin, total	Magnesium
Blood urea nitrogen (BUN)	Phosphorous
Calcium, total	Potassium
Carbon dioxide, total (bicarbonate)	Protein, total
Chloride	Sodium

Alanine aminotransferase (ALT)	Creatinine, serum
Creatine phosphokinase	Low density lipoprotein (LDL) cholesterol
Uric acid	High density lipoprotein (HDL) cholesterol
Cystatin C	triglycerides

Hematology

The hematology parameters in [Table 4](#) will be assessed at every visit.

Table 4: Hematology Parameters

Platelet count	Automated WBC Differential:
RBC count	Neutrophils
WBC count (absolute)	Lymphocytes
Hematocrit	Monocytes
Hemoglobin	Eosinophils
	Basophils

Urinalysis

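### Protocol 8.2.5 exempts expected Fabry-related findings from AE reporting while 7.6, 8.2.12.1 and 8.2.12.4 require an AE, so AE and AE-discontinuation counts can differ by site

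*Protocol*

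**What the plan says.** The protocol sets AE recording rules in several places.

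- **8.2.5, general rule.** Abnormal laboratory results and other safety assessments "felt to be clinically significant in the medical and scientific judgment of the investigator are to be recorded as AEs or SAEs".
- **8.2.5, exception.** The next paragraph removes from reporting "any clinically significant safety assessments that are associated with the underlying disease, unless judged by the investigator to be more severe than expected" for that subject's condition.
- **7.6.** If study drug is interrupted or discontinued because of an AE, "an abnormal assessment (e.g., ECG finding), or a laboratory test abnormality, this information will be recorded as an AE".
- **8.2.12.4.** "Clinically significant laboratory abnormalities must be reported as an AE or SAE as appropriate".
- **8.2.12.1.** A clinically significant physical finding that is new or worse since the "first dose of study medication in the current study, should be reported as an AE".
- **8.2.4.1.** Changes in the disease may fall outside the AE definition, but "if there is a clinically relevant worsening of a sign or symptom of the condition under treatment" and the AE definition is met, reporting is mandatory.
- **8.2.12.3.** For ECGs: "Significant findings not present prior to start of treatment, which meet the definition of an AE, must be recorded in the CRF".

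SAP 18.1 tabulates AEs as recorded. SAP 18.1.2 identifies AEs leading to discontinuation solely from the AE form, through the entry showing that study drug was permanently stopped. The SAP has no rule for disease-related findings.

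**The concern.** The primary objective is long-term safety, and AEs head the list of safety assessments in 8.2.1. Protocol 3.2 describes declining renal function as typical of Fabry disease, so findings that could fall under the 8.2.5 exception are to be expected in this population. If sites may reasonably follow different sections, the same creatinine rise is an AE at one and not at another. There is no comparator arm in which the same recording difference would appear.

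The sharpest consequence is for discontinuations. A subject taken off drug for a renal measurement, with no AE form completed, would be missing from the table meant to show who stopped because of an adverse finding.

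**Working it through.** No plan figure can be reproduced: the documents give no hypothesis test, no sample size calculation and no expected AE rate. The check is a comparison of the rules, followed by their path into the outputs.

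**Step 1. The rules side by side, for a clinically significant finding linked to Fabry disease and of expected severity.**

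| Protocol section | Trigger | Disease exception or cross-reference to 8.2.5? | AE? |
|---|---|---|---|
| 8.2.5, second paragraph | Associated with the disease, no worse than expected | It is the exception | No |
| 7.6 | Abnormality causes interruption or discontinuation | None | Yes |
| 8.2.12.4 | Clinically significant laboratory result | None | Yes |
| 8.2.12.1 | Clinically significant physical finding, new or worse | None | Yes |
| 8.2.4.1 | Clinically relevant worsening that meets the AE definition | Different test | Depends |
| 8.2.12.3 | Significant new ECG finding that meets the AE definition | Conditional | Depends |

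One section prohibits and three require. The last two are conditional and are not direct conflicts, but 8.2.4.1 asks whether worsening is clinically relevant while 8.2.5 asks whether severity exceeds expectation. A slow decline can be clinically relevant and still expected, so the two tests can give different answers.

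**Step 2. A case from the plan's own criteria.** Protocol 8.2.2 requires withdrawal for a confirmed 30% rise in serum creatinine from Visit 1 or for an eGFR below 30 mL/min/1.73m². Exclusion criterion 1 in 6.3 bars entry below 30 but not just above it. A subject who enters a little above 30 and declines at the expected pace reaches the eGFR criterion without anything worse than expected having happened. Under 8.2.5 this finding is not an AE. Under 7.6 it is, because it is the reason for stopping drug. Under 8.2.12.4 it is if the investigator calls the laboratory result clinically significant.

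**Step 3. Which outputs depend on the answer.**

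- Dependent on an AE record: AE incidence (SAP 18.1 and 18.1.1) and AEs leading to discontinuation (SAP 18.1.2).
- Not dependent: by-visit eGFR (SAP 17.1), laboratory shift tables and investigator-flagged laboratory results (SAP 18.4.1), ECG clinical-significance tables (SAP 18.5), ECHO categories (SAP 18.6), and disposition (SAP 10), which has a reason for meeting a protocol stopping criterion separate from the AE reason.

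**Step 4. Scale per subject.** Protocol 6.1 expects up to 100 subjects. Assuming all 100 are in the ITT population:

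- one subject recorded under one rule but not the other changes a term's incidence by 1/100 = 1.0 percentage point;
- five such subjects give 5/100 = 5.0%, enough by themselves to bring a preferred term into the SAP 18.1.1 table of AEs in 5% or more of subjects.

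With N subjects the step is 1/N, so it grows if fewer enrol. This is the effect per affected subject, not an estimate of how many there are.

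**The case against.** **The sections can be read together.** Section 8.2.5 deals specifically with abnormal results as AEs, states the general rule and then limits it. Section 8.2.12.4 can be taken as a restatement subject to that limit. This is a fair reading, and it narrows the dispute to findings of expected severity. It does not settle 7.6, which has its own specific trigger and is at least as specific for discontinuations. No section states the precedence that this reading needs.

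**A finding that forces withdrawal is hardly of expected severity.** Many investigators would record a confirmed 30% creatinine rise as an AE. That weakens the creatinine example more than the eGFR one, where a small expected decline can cross the line.

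**The study manual may contain a working rule.** Protocol 8.2.11 places the method of recording AEs in the SPM/ISFN, which is not available here. This stands as a limit: the text permits sites to differ, but it cannot be shown that they do.

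**Stronger readings that the documents do not support.**

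- A reader might infer that a primary safety endpoint turns on this. The documents name a primary objective, not a primary endpoint, and several safety outputs do not use AE records.
- A reader might infer that the exception covers the disease's main long-term risks, stroke included. Section 8.2.5 concerns laboratory results and other safety assessments. A stroke or clinical cardiac event falls under the AE and SAE definitions in 8.2.4.1 and 8.2.4.2.
- A reader might want an estimate of the share of AEs lost. The documents give no basis for one.

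**Conclusion.** The contradiction is in the current protocol text and should be removed. It is confined to clinically significant assessments that the investigator links to Fabry disease and judges no worse than expected. It is clearest between 8.2.5 and 7.6, where following the plan as written can leave subjects out of the AE-discontinuation table. The renal and cardiac signals are not lost, because they remain visible in the measurement and disposition outputs. Those outputs do not correct the AE counts, however. The number of subjects affected is unknown. The conclusion assumes that no rule outside these documents already settles precedence.

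**What to change.** Reconcile the passages with one recording rule:

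1. State in 8.2.5 that its exception does not apply when the finding leads to interruption or discontinuation of study drug, which 7.6 already requires.
2. Cross-refer 8.2.12.1 and 8.2.12.4 to 8.2.5, so that the exception is either visible there or expressly excluded.
3. Align the 8.2.5 severity test with the worsening test in 8.2.4.1.
4. For data already collected, add an SAP listing of subjects who met a stopping criterion, or discontinued for an abnormality, without a matching AE record. The disposition, laboratory and ECHO data already planned can identify those who met a measured stopping criterion.

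This concerns recording only and changes no stopping rule or treatment. Requiring an AE for every new or worsened finding whatever its link to Fabry disease would go further than the contradiction demands: it would largely abolish the exception, which is a separate policy choice.

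The cost is a protocol wording change, one listing and slightly more AEs recorded. AE capture before and after the amendment may not be fully comparable; the listing makes that difference visible.

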8.2.6. Possible Suicidality Related Adverse Event(s) (PSRAE)

The PSRAE eCRF form should be completed (in addition to the AE or SAE pages, as appropriate) if there is an occurrence of an adverse event which, in the investigator's opinion, is possibly related to suicidality. This may include, but is not limited to, an event that involves suicidal ideation, a preparatory act toward imminent suicidal behavior, a suicide attempt, or a completed suicide. The investigator will exercise his or her medical and scientific judgment in deciding whether an event is possibly related to suicidality. The investigator will record this information in the source document and the PSRAE eCRF. The PSRAE form should be completed in its entirety as soon as the information is available and updated with any additional follow-up information received.

If the adverse event meets the definition of an SAE, the investigator must ensure that there are no discrepancies between the PSRAE and SAE forms. Both forms (PSRAE and SAE) should be updated with any follow-up information.

8.2.7. Pregnancy

Any pregnancy that occurs during study participation must be reported using a notification of pregnancy form. To ensure subject safety, each pregnancy must be reported to Amicus within 5 days of learning of its occurrence. The pregnancy must be followed up to determine outcome (including premature termination) and status of mother and child. Pregnancy complications and elective terminations for medical reasons must be reported as an AE or SAE. Spontaneous abortions must be reported as an SAE.

Any SAE occurring in association with a pregnancy, brought to the investigator's attention after the subject has completed the study and considered by the investigator as possibly related to the study treatment, must be promptly reported to Amicus.

In addition, the investigator must attempt to collect pregnancy information on any female partners of male study subjects who become pregnant while the subject is enrolled in the study. Pregnancy information must be reported to Amicus as described above.

8.2.8. Reporting of Overdose

Any event associated with or observed in conjunction with a product overdose (whether accidental or intentional) is considered by the sponsor to be an AE and must be reported as such. If a subject experiences an overdose (defined as higher than the dose of study medication prescribed in the protocol) during the course of the study (whether symptomatic or not), the sponsor must be informed within 5 working days of the investigator or study staff first becoming aware of the overdose. Follow-up information must be forwarded on the outcome as applicable. If an SAE occurs in conjunction with the overdose, then the reporting time frame for an SAE as described below must be met.

8.2.9. Reporting of Possible Study Drug Product Quality Complaints

Any defect or possible defect associated with the study medication provided by the sponsor must be reported by the investigator or study staff to the sponsor within 1 working day of first becoming aware of the possible defect. The study medication and packaging components in question, if available, must be stored in a secure area under the specified storage conditions until it is determined whether the study medication and/or

packaging is required for investigation of the possible defect. If the possible defect is associated with an SAE, the SAE must be reported as described below. The SAE report form must mention the possible study medication defect complaint.

8.2.10. Time Period and Frequency of Detecting AEs and SAEs

The investigator or site staff is responsible for detecting, documenting, and reporting events that meet the definition of an AE or SAE.

AEs will be collected from the start of the subject's first dose of study medication in the current study and until the follow up contact or 30 days after last dose, whichever comes first.

SAEs will be collected over the same time period as stated above for AEs. However, any SAEs assessed **as related** to study participation (e.g., study treatment, protocol-mandated procedures, invasive tests, or change in existing therapy), will be recorded from the time a subject consents to participate in the study up to and including any follow up contact. All SAEs will be reported to Amicus within 24 hours, as indicated in Section [8.2.11](#).

8.2.11. Prompt Reporting of Serious Adverse Events and Other Events to Amicus

SAEs, pregnancies, medical device incidents and liver function abnormalities meeting pre-defined criteria will be reported promptly by the investigator to Amicus as described in the following table once the investigator determines that the event meets the protocol definition for that event.

Table 2: SAE and Pregnancy Reporting Time Frames

Type of Event	Initial Reports		Follow-up Information on a Previous Report	
	Time Frame	Documents	Time Frame	Documents
All SAEs	24 hours	“SAE” data collection tool	24 hours	Updated “SAE” data collection tool
Pregnancy	5 days	“Pregnancy Notification Form”	5 days	“Pregnancy Follow-up Form”
Liver chemistry abnormalities for Phase III to IV:				
ALT \geq 3xULN and Bilirubin \geq 2xULN (>35% direct) (or ALT \geq 3xULN and INR $>$ 1.5, if INR measured) ¹	24 hours ²	“SAE” data collection tool. “Liver Event eCRF” and “Liver Imaging” and/or “Liver Biopsy” eCRFs, if applicable ³	24 hours	Updated “SAE” data collection tool/“Liver Event” Documents ³
ALT \geq 8xULN; ALT \geq 3xULN with hepatitis or rash or \geq 3xULN and <5xULN that persists \geq 4 weeks	24 hours ²	“Liver Event” eCRF ³	24 hours	Updated “Liver Event” eCRF ³
ALT \geq 5xULN plus bilirubin <2xULN	24 hours ²	“Liver Event” eCRF do not need completing unless elevations persist for 2 weeks or subject cannot be monitored weekly for 2 weeks ³	24 hours	Updated “Liver Event” eCRF if applicable ³
ALT \geq 5xULN and bilirubin <2xULN that persists \geq 2 weeks	24 hours ²	“Liver Event” Documents (defined above) ³	24 hours	Updated “Liver Event” eCRF ³
ALT \geq 3xULN and <5x ULN and bilirubin <2xULN	24 hours ²	“Liver Event” eCRF do not need completing unless elevations persist for 4 weeks or subject cannot be monitored weekly for 4 weeks ³	24 hours	Updated “Liver Event” eCRF, if applicable ³

¹ INR measurement is not required; if measured, the threshold value stated will not apply to patients receiving anticoagulants.

² Amicus must be contacted at onset of liver chemistry elevations to discuss subject safety.

³ Liver Event Documents should be completed as soon as possible.

ALT = alanine aminotransferase, eCRF = electronic case report form, INR = international normalized ratio, SAE = serious adverse event, ULN = upper limit of normal

The method of detecting, recording, evaluating, and follow-up of AEs and SAEs plus procedures for completing and transmitting SAE reports to Amicus are provided in the SPM/ISFN. Procedures for post-study AEs/SAEs are provided in the SPM/ISFN.

Procedures for documenting, transmitting, and follow-up of medical device incidents along with the regulatory reporting requirements for medical devices are provided in the SPM/ISFN.

